#### Instructions to Subjects at the End of Each Stage:

We will provide the following instructions about continued marijuana use at the end of the study to facilitate safety:

Cannabis (marijuana) is composed of many substances. Street cannabis is high in tetrahydrocannabinol (THC), which causes the “high” feeling. Street cannabis has lower concentrations of cannabidiol (CBD). The cannabis preparations sold at dispensaries have various concentrations of THC and CBD. The ratio of THC to CBD plays a role in a preparation’s beneficial and adverse effects. Studies to date suggest that THC is especially risky in person with PD, because it may worsen thinking and coordination and cause psychiatric symptoms. The precise effects of all the substances in cannabis is unknown. In this study we are using Epidiolex. It is >99% pure CBD with only a trace amount of THC (<0.15%) and it has more data regarding safety, tolerability, dosing and efficacy than most other forms. Using marijuana should be under the supervision of your physician, with monitoring the symptoms of PD and other diseases, as well as the interactions of marijuana and other drugs you take.

#### **C.5 Randomization and drug dispensation:**

Patients who consent will be stratified by age (45 – 60 and 61-78) and disease severity (H&Y 1 – 2.5, 3 – 5) and divided into blocks of a few patients each, depending on order of recruitment. Equal numbers from each block will be assigned to each of two sequence groups. One group will receive the control first and the treatment second, and the other group will receive the treatment first and the control second. Since all subjects receive both treatments randomization and stratification are less critical than in studies with fixed treatment groups, unless order effects are important or an expectedly large number of patients drop out.

The study drug, Epidiolex, and matching placebo will be provided by GW Pharmaceuticals. GW will ship the drug according to British and US regulations. Initially enough study drug will be provided for the Stage 1 open label study, and replenishment shipments will follow. [name], the PI, will obtain a Schedule 1 license and all procedures of drug handling will be according to DEA specifications. Briefly, designated study personnel will receive the study drug, store it, measure and label it ([name] and her fellow) and dispense to the subject (study coordinator).

#### **C.6 Blinding assessment and Un-blinding procedures:**

##### **Blinding assessment:**

Active drug and placebo will look and taste the same. Subjects and all study personnel except for Drs. [name], [name] and her fellow, are blinded.

During each visit when on study drug and at the safety follow up visit, participants will be asked

about the treatment allocation they think they were assigned. The answers are taken in forms with five responses of “strongly believe the treatment is drug”, “Somewhat believe the treatment is drug”, “Somewhat believe the treatment is placebo”, “Strongly believe the treatment is placebo”, and “Don’t know”.

### **Un-blinding procedures:**

The identity of the treatment assigned to individual subjects can be revealed in an emergency only. The PI is responsible for ensuring that the instructions on how to request unblinding of treatment are stored safely, that their location is known, and that access is readily available to the relevant staff in case of an emergency. [name], the statistician will provide the information when un-blinding is requested by the PI. As a back up, [name] will provide a file of sealed envelopes to the PI, which is kept in a locked file in her office. The location is known to the PI, sub-I and coordinator. A sealed envelope coded with each subject number is provided. In the event that [name] is not available to provide break the blind the PI and designated staff can do so.

A subject’s treatment assignment should only be un-blinded when knowledge of the treatment is essential for the safety of the subject. Un-blinding for any other reason will be considered a protocol deviation.

### **C.7 Stopping rules:**

Note there are no interim analyses planned.

### **Participant stopping rules (Both Stages):**

- If subject cannot tolerate the study drug at any dose level
- if subject develops a CTCAE criteria grade 3 or 4 adverse event per that the Investigator determines is related the study drug
- Pregnancy or breast-feeding
- Requested by subject to terminate treatment
- Failure by the subject to attend consecutive study visits;
- Subject is at significant risk of failing to comply with the provisions of the protocol as to cause harm to self or seriously interfere with the validity of the study results;
- At the discretion of the IRB, Food and Drug Administration (FDA).

If a subject is withdrawn from the study, all efforts will be made to complete the early termination visit that includes efficacy assessments and safety follow-up. In addition, women of childbearing potential will have a post-study pregnancy test performed at the early termination visit.

Withdrawals and the reason for withdrawal will be tabulated by treatment group. The number and percentage of subjects who complete the study will be summarized by treatment group. The number and percentage of subjects who withdraw from the study will be tabulated by original treatment group and last treatment taken at time of withdrawal. Study medication discontinuations will be summarized in a similar fashion.

Subjects will be advised that they are free to withdraw from the study at any time. Reasons that subjects may be withdrawn from the study include the following:

Subject discontinued study medication and wishes to withdraw.

Subject consent is withdrawn.

### **Study stopping rules (Both Stages)**

- Subjects are unable to be recruited
- Study drug becomes unavailable
- Subjects are unable to tolerate the study drug at any dose level
- Discovery (from this or other studies) of an unexpected, serious, or unacceptable health hazard to subjects, i.e., development of the same adverse event, CTCAE criteria grade  $\geq 3$ , related to study drug in  $\geq 2$  subjects
- At the discretion of the IRB, Food and Drug Administration (FDA).

Any of the above occurring during Stage 1 will lead to a hold and reassessment of starting Stage 2.

### **C.8 Adverse events assessments:**

Adverse events will be classified according to ICH Good Clinical Practice (GCP) definitions. Any adverse event or abnormal laboratory test value that is serious (see definition below) and occurs after administration of the investigational product will be documented by the Sponsor-Investigator within 24 hours of discovery of the event.

#### **Severity of Adverse Events**

The severity of each AE/SAE will be classified into one of three defined categories as follows:

- Mild: the AE is easily tolerated by the subject, causes minimal discomfort, and does not interfere in a significant manner with the subject's normal functioning level or activities;
- Moderate: the AE is sufficiently uncomfortable to interfere with normal everyday activities, but is not hazardous to health;
- Severe: the AE produces significant impairment of functioning or incapacitation and is a definite hazard to the subject's health.

These three categories are based on the investigator's clinical judgment, which in turn depends on consideration of various factors such as the subject's reports, the physician's observations, and the physician's prior experience. The severity of the AE will be recorded in the appropriate section on the AE page of the CRF.

#### **Serious Adverse Events (SAEs)**

The evaluation of severity will be distinguished from the evaluation of "seriousness". A severe event might not meet the criteria for seriousness and a serious event might be evaluated as mild or moderate. For example, a subject might have a severe headache that does not require hospitalization and is consequently not serious; or a subject might have a mild myocardial infarction that requires hospitalization and is therefore serious.

An SAE is any untoward medical occurrence at any dose that:

- Results in death during the period of protocol-defined surveillance. Death due to PD will not be considered an SAE. However, if a patient requires hospitalization due to an AE related to PD, the specific sign or symptom leading to hospitalization will be reported as an SAE. If death due to PD occurs outside of hospitalization and is considered to be due solely to the patient's PD, no SAE report is required. The death will be recorded as part of PD and patient disposition.
- Is life-threatening (NOTE: The term "life-threatening" in the definition of "serious" refers to an event in which the subject, in the view of the Investigator, is at risk of death at the time of the event; it does not refer to an event that hypothetically might cause death if it was more severe)
- Requires inpatient hospitalization or prolongation of existing hospitalization\*
- Results in persistent or significant disability or incapacity
- Results in a congenital anomaly/birth defect.

\* Hospitalization: Out-patient treatment in an emergency room is not in itself an SAE, although the reasons for it might be (e.g., bronchospasm, laryngeal edema). Hospital admission and/or surgical operations planned before or during a study are not considered SAEs if the illness or disease existed before the subject was enrolled in the study, provided that it did not deteriorate in an unexpected way during the study. It should be noted that for this study, subjects with planned or anticipated surgery should not be enrolled into the study.

Important Medical Events: Medical and scientific judgment will be exercised in deciding whether a case is serious in situations where important medical events may not be immediately life-threatening or result in death, hospitalization, disability, or incapacity but may jeopardize the subject or may require medical or surgical intervention to prevent one or more outcomes listed in the definition of serious. These should usually be considered as serious, and examples of such events are:

- Angioedema not severe enough to require intubation but requiring intravenous hydrocortisone treatment
- Hepatotoxicity caused by paracetamol (acetaminophen) overdose requiring treatment with N-acetylcysteine
- Intensive treatment in an emergency room or at home for allergic bronchospasm
- Development of drug dependency or drug abuse.

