Extensive reports of CBD administration across a wide range of concentrations did not detect important adverse or toxic effects [Bergamaschi MM, et al. 2011]. With a median Lethal Dose (LD50) of 212 mg/kg in rhesus monkeys, CBD has a low toxicity [Rosenkrantz H, et al. 1981]. Some studies investigated mutagenic or teratogenic effects and describe no such events [Matsuyama SS, Fu TK. 1981; Dalterio S, et al. 1984]. We reviewed the tolerability of CBD doses used in human studies to date – one study suggested over 300 mg per day may exacerbate bradykinesia [Consroe P, et al. 1986], but other studies used 7.5 to 1500 mg per day without significant adverse effects [Bergamaschi MM, et al. 2011; Zuardi AW, et al. 1995]. Most studies used doses in the range of 200 - 600 mg/day.

In this study we are using Epidiolex, which is >99% pure CBD with only a trace amount of THC (<0.15%). GW conducted a single ascending dose study in which four groups of six healthy volunteers received single oral doses of either 1500mg, 3000mg, 4500mg or 6000mg purified CBD oral solution (Ref: GWEP1544 safety assessment following dose administration of cannabidiol to healthy volunteers, 2015). Each single oral dose was well tolerated. In a 70kg individual these doses are equivalent from 21 mg/kg to 85mg/kg in a single daily dose. Currently Epidiolex is being used in four FDA approved epilepsy studies. GW has determined a dose range that is best tolerated and effective in psychosis and seizure disorders. These studies are described in the Investigational Brochure (IB) Edition 8, Section 7.3.1. Open label study results have recently been published and are described in section C.1.

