## Potential drug-drug interactions

The PI has worked with [name], Pharm D, and GW to study possible drug interactions. See GW Pharmaceutical's Investigator Brochure on CBD, especially pages 4-5, 47-51 and 105-106 and their CBD;CBD BDS Development Core Safety Information dated August 2015 pages 2-4 for detailed information. Also, Appendix 2 is a list of drugs with potentially interactions with CBD, thus the PI will monitor for clinical effects. CBD concentrations and adverse events will be monitored in the presence of concomitant medications which are inhibitors of CYP3A4 and 2C19.

There are many possible interactions, but some are more likely and clinically relevant. Thus, the PI will especially monitor for clinical symptoms that may be associated with these particular interactions. The following drugs may increase the level of CBD: fluoxetine, fluvoxamine, fluconazole, ticlopidine and nefazodone. The following drugs may decrease the level of CBD: carbamazepine, phenytoin, phenobarbital, rifampin and St. John's Wort. The following drugs may interact with CBD to cause their levels to increase: alprazolam, clonazepam, lorazepam, oxazepam, temazepam, zolpidem, clopidogrel, narcotics (codeine, methadone, oxycodone, hydromorphone, morphine), cyclosporine A, tacrolimus, propranolol and acetaminophen. Subjects will be instructed not to take more than 1 gram per day of acetaminophen.

CBD is a potent inhibitor of CYP2C19. The plasma level of clobazam, which is metabolized by CYP2C19, therefore is expected to increase if CBD is added. Clobazam, per Micromedex, causes somnolence (16-25%). In a recent study, *Lancet Neurology* 2016;15:270-278, using the same study drug as in our trial at similar doses there was ~twice as much somnolence AEs reported in subjects on both CBD and clobazam than in subjects on CBD and not clobazam. Thus clobazam will be exclusionary in this study.

The following is additional information relevant to the population of this study, Parkinson disease (PD).

CBD is metabolized by the hepatic CYP450 enzymes 2C19 and 3A4 and an inhibitor of these isoenzymes. Thus the expectation is that selegiline levels could increase. CBD may mildly induce the expression of 1A2, 2B6, and 3A4. Thus the expectation is that levels of rasagiline, ropinirole and selegiline may decrease.

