CBD is a relatively potent inhibitor of UGT1A9 and UGT2B7 and has no significant effect on other UGT isoenzymes. The expectation is that the level of rotigotine may increase.

CBD is highly protein bound, so rasagiline, selegiline and rotigotine levels may increase transiently.

Checking plasma concentration levels of these anti-PD medications is not a routine clinical practice. Thus the PI will monitor subjects on these medications for clinical changes. The most important and likely adverse effects of a clinically significant increase in the level of selegiline is anxiety, dyskinesia, agitation, insomnia and hallucinations. The most important and likely adverse effects of a clinically significant decrease in the levels of rasagiline, ropinirole and selegiline is an increase in the motor symptoms of Parkinson disease, which are resting tremor, bradykinesia, rigidity and postural instability. The most important and likely adverse effects of a clinically significant increase in rotigotine is low blood pressure, somnolence and impulse control disorders.

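### The SAE definition exempts deaths attributed to Parkinson disease without requiring a relatedness assessment, so a drug-related death misattributed to PD could escape causality review

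*Combined protocol and SAP*

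**What the plan says.** Section IV.C.8, Serious Adverse Events, makes death during the surveillance period an SAE and then qualifies this in four steps:

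- A general exemption: "Death due to PD will not be considered an SAE".
- A limit for patients admitted with a PD-related event: "the specific sign or symptom leading to hospitalization will be reported as an SAE".
- A waiver for a death outside hospital that is "considered to be due solely to the patient's PD, no SAE report is required".
- A place to file it: "The death will be recorded as part of PD and patient disposition".

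Elsewhere the protocol says that the drug may affect the disease itself:

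- Section III: "one study suggested over 300 mg per day may exacerbate bradykinesia".
- Section IV.C.4, on drug interactions: "Thus the expectation is that levels of rasagiline, ropinirole and selegiline may decrease". The stated consequence of such a decrease "is an increase in the motor symptoms of Parkinson disease".
- Section IV.C.9 lists extrapyramidal symptoms among the side effects.

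Sections IV.A (Stage 2, primary outcome, item 3) and F count the MDS-UPDRS and other motor assessments among the primary safety measures.

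**The concern.** Whether a decline in PD on CBD is disease or drug is one of the questions the primary safety aim is meant to answer. The SAE section lets an attribution to PD settle that question when the death is classified, before the relatedness criteria are applied and with no record required of how the attribution was made. The gradient is also odd: a PD sign that leads to admission is an SAE, while a PD death at home may need no report. At stake is whether a death to which the drug contributed, but which was put down to PD, would be examined for causality at all.

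**Working it through.** The plan states no figure on this point, so the check is mainly a comparison of text, followed by two supporting calculations.

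**1. What the SAE section does with each kind of PD death**

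| Death | General sentence | Later sentences |
|---|---|---|
| In hospital, attributed to PD | Not an SAE | The sign or symptom that led to admission is an SAE |
| Outside hospital, due solely to PD | Not an SAE | No SAE report; filed as disposition |
| Outside hospital, due partly to PD | Not an SAE, if read as due to PD | Not covered by the waiver |

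The third row is ambiguous: the general sentence is broader than the waiver. None of the rows carries a requirement to assess relatedness of the death.

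**2. Where a misattributed death would go next**

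- *Relationship to Study Drug (IV.C.8).* An AE or SAE counts as related unless a not-related criterion is met. Natural history of the underlying disease is one of the alternative causes to be weighed. A death held only as disposition is neither an AE nor an SAE, so this assessment is not triggered.
- *15-day report.* It needs a serious, unexpected event considered reasonably or possibly related. The exemption removes seriousness by death, and no relatedness judgement exists.
- *7-day report.* It needs a fatal or life-threatening adverse event, unexpected and possibly related. The SAE label does not matter, but the death must be recorded as an adverse event and assessed.
- *Study stopping rule (IV.C.7).* It needs the same drug-related event, CTCAE grade 3 or higher, in at least two subjects. Section IV.C.2 makes death related to an AE grade 5, so a fatal case could be one of the two. Again the input is a related adverse event, not SAE status.

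**3. Is the cited motor signal in the dose range studied?** At 70 kg, the weight used in section III, 5 mg/kg/day is 5 × 70 = 350 mg/day and 20 mg/kg/day is 20 × 70 = 1,400 mg/day. Stage 2 text and schedule also mention 25 mg/kg/day: 25 × 70 = 1,750 mg/day. All exceed the 300 mg/day in the remark. At 50 kg the starting dose does not: 5 × 50 = 250 mg/day.

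**4. Expected number of deaths.** The documents give no mortality rate; 1–3% per year is an assumption. Stage 2 has 50 subjects (sections I and IV.C.1), and the schedule ends on day 133, or 133/7 = 19 weeks.

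- All of Stage 2: 50 × 19/52 × 0.01 = 0.18 and 50 × 19/52 × 0.03 = 0.55 deaths from any cause. With the 48 subjects of the sample size section the result is 0.18 to 0.53.
- About 7 weeks on CBD: 50 × 7/52 × 0.01 = 0.067 and 50 × 7/52 × 0.03 = 0.20.
- Chance of two or more deaths from any cause on CBD, Poisson with mean m: 1 − e^(−m)(1 + m) = 0.2% at m = 0.067 and 1.8% at m = 0.20.

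Deaths that are attributed to PD, outside hospital and in truth drug-related would be a small part of these counts.

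**The case against.** The case on the other side is substantial.

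- **The waiver has two conditions.** A reader might infer that any PD death at home goes unreported. The text also requires that it be due *solely* to PD. A death in which the drug is suspected does not qualify, so the gap opens only through misattribution. That stands. The fix would not change who judges, but it would require the judgement to be made and recorded.
- **A PD-attributed death does not necessarily miss every downstream rule.** The stopping rule and the 7-day report are not tied to SAE status. That stands; the supportable word is could.
- **Worsening before death is watched.** Life-threatening events and disability remain SAE criteria, phone calls recur every 3rd or 10th day, a related grade 3 or 4 event ends that participant's treatment, and a DSMB and the IRB oversee the study. Section IV.C.7 also tabulates withdrawals by treatment group. These reduce the risk, but none requires a causality assessment of a death outside hospital put down to PD.
- **The motor evidence is mixed.** Section III also reports studies at up to 1,500 mg/day without significant adverse effects, and a small PD study in which motor function did not worsen. The decrease in levels concerns three named drugs, and selegiline levels might also rise. That stands: the documents raise motor worsening as a possibility and nowhere suggest fatal worsening.
- **Conflict with the ICH statement.** A reader might infer that the exemption contradicts the opening of IV.C.8, "Adverse events will be classified according to ICH Good Clinical Practice (GCP) definitions". The documents do not reproduce the ICH definition, and that paragraph refers to the protocol's own definition of serious. No contradiction can be shown from them.

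**Conclusion.** The point holds in a limited form. The exemption is a stated rule, broader in its first sentence than in its waiver, and it leaves a death attributed to PD without a required relatedness assessment in a trial whose protocol names motor worsening as a possible drug effect. The consequence is conditional on a drug-related death being misattributed to PD and recorded only as disposition.

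The probability is low. Fewer than one death from any cause is expected under the assumed 1–3% mortality, and two deaths on CBD are unlikely. A single misfiled death could still matter to the stopping rule if another subject had the same related event at grade 3 or higher. The primary analysis is not undermined. The case for change rests on negligible cost against a rare but serious loss of safety information.

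**What to change.** In IV.C.8, Serious Adverse Events, delete the general exemption for PD deaths and the sentence that waives the report. State that every death in the surveillance period is recorded as an SAE, with relatedness assessed under Relationship to Study Drug. It can still be listed under disposition as well. Then make the study stopping rules in IV.C.7 and the 7-day and 15-day reporting paragraphs consistent with this, so that it is clear how a death enters each. No threshold, dose or treatment rule needs to change. The cost is a wording amendment and, given the expected counts, at most one or two additional reports.

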### Unanticipated Adverse Events

An unanticipated problem is any event or information that was unforeseen and indicates that the research procedures caused harm (including physical, psychological, economic, or social harm) to participants or others or indicates that participants or others are at increased risk of harm than was previously known or recognized. An "unexpected" adverse reaction is one in which the nature or severity of which is not consistent with information in the relevant source document(s). Until source documents are amended, expedited reporting is required for additional occurrences of the reaction.

